**2. Project Title:**

Cross-cultural adaptation and validation of the pediatric chemotherapy-induced neuropathy (P-CIN) for Chinese pediatric oncology patients: A methodological and descriptive study

**3. Project Objectives: (Purpose of proposed investigation)**

This study aims to cross-culturally adapt and validate the original P-CIN for Chinese pediatric oncology patients.

**4. Scope and Background of Research:**

(Please identify key issues/problems to be addressed)

Chemotherapy-induced peripheral neuropathy (CIPN), one of the most common adverse effects of neurotoxic chemotherapeutic agents, has been defined as a single, or a combination of motor, sensory and autonomic impairments that results from the damage, inflammation, and degeneration of peripheral nerve fibers. CIPN is a marker of multiple serious consequences, including decreased physical activity, falling, pain, fatigue, sensory and motor deficits, poorer quality of life, mortality, and psychological distress. The development of CIPN may lead to dose reduction, interruption or cessation of the chemotherapy treatment, which can impact the treatment efficacy and decreasing their survival.[1] Clinical abnormalities attributable to CIPN including sensory and motor neuropathy, functional deficits and CIPN pain are common in pediatric oncology patients and can persist into adulthood. Systematic review has reported that CIPN incidence in pediatric patients varies from 2.8% to 100% depending on the assessment measures.[1] Therefore, it is crucial to accurately identify and assess CIPN at the earliest possible stage.

The severity of CIPN may fluctuate during treatment courses, the overall trend tends to show increasing severity, even as dose intensity and treatment frequency may decrease over time. In addition, CIPN may last for months to several years after the end of anticancer chemotherapies.[2] Thus, early identification is imperative for the intervention implementation that can improve long term care and relieve disease burden. There is limited evidence to a feasible, simple and accurate assessment measure for pediatric CIPN and

numerous CIPN measures have been developed. According to our previous updated systematic review, the Total Neuropathy Score (TNS) variants including Pediatric-modified Total Neuropathy Score (Ped-mTNS) and Total Neuropathy Score-Pediatric Vincristine (TNS-PV), as an objective measure, is the most widely used assessment measure of CIPN. However, both have limitations associated with the pediatric oncology patients in clinical settings. The Ped-mTNS includes many physical examinations, such as light touch sensation, pin sensibility, vibration sensation, and strength and deep tendon reflexes. These measurements are not only the time-consuming and clinical space using for assessments but also induce discomforts associated with some testing procedures, e.g., pin prick. The TNS-PV is only for assessing CIPN severity in children taking Vincristine. In addition, a trained registered clinician performs these two measurements. Hence, the Ped-mTNS and TNS-PV maybe not feasible to be used widely in the clinical settings in China. Other pediatric CIPN assessment measures, the Functional Assessment of Cancer Therapy-Gynecologic Oncology Group-Neurotoxicity (FACT-GOG-Ntx) only validated in pediatric patients with Hodgkin lymphoma and the Bruininks-Oseretsky Test of Motor Proficiency version 2 (BOT-2) only used to assess the motor skills in pediatric patients with CIPN. Thus, these assessment measures cannot comprehensively evaluate the CIPN severity in pediatric oncology patients. Furthermore, the few existing pediatric CIPN measures are not well validated.

There is a critical need for pediatric CIPN measures. The Pediatric Chemotherapy-Induced Neuropathy (P-CIN), which includes the core elements of CIPN symptoms, was specially developed for assessing CIPN severity in pediatric patients. The P-CIN consists of 13 self-reported items using age-appropriate language and graphics without involving clinician examination, and it takes only a few minutes and can be completed by pediatric patients themselves or their parents' assistance. The P-CIN can be feasibly applied by pediatric oncology patients themselves or their parents in China where healthcare service space and service time lacking and short-staffing of pediatricians. In turn, the P-CIN helps in the early identification of CIPN in pediatric oncology patients and evaluate the effectiveness of an intervention.

The original P-CIN was developed in 2021 and the first electronic CIPN patient reported outcome measure (PROM). The European Organisation for Research and Treatment of Cancer Quality of Life Questionnaire - Chemotherapy-Induced Peripheral Neuropathy 20-item sub-scale (EORTC QLQ-CIPN20) served as a model when developing P-CIN specific items, and further validated in pediatric patients with CIPN in the United States. The P-CIN contains four items to rate CIPN subjective symptoms - numbness and tingling in the hands and feet. If pediatric patients reported experiencing these symptoms, they were directed to answer four additional questions regarding painful numbness and tingling. Five items were used to quantify CIPN functional deficits experienced such as picking up a penny or heel-

walking. Evidence indicates that the P-CIN is reliable and valid in United States context. However, there is a lack of measures for CIPN assessment in China after a systematic search and the P-CIN has never been validated for use with pediatric patients with CIPN in China. This lack of validated assessment measures preclude understanding the severity of the CIPN and hinders the development of appropriate interventions to promote CIPN symptoms management. On the other hand, a culturally sensitive assessment is critical in defining, identifying, describing and understanding the signs and symptoms of CIPN[3] as the culture and language can impact the expression and interpretation of symptom characteristics.[4] For instance, in East Asia, terms like “burning” were never used, with patients may report “numbness”.[4, 5] Due to the aforementioned concerns, it may be not appropriate to apply the P-CIN to assess the CIPN severity of pediatric patients before cross-cultural adaptation and validation. It is essential that assessment measures are appropriately adapted and validated in a new cultural setting to ensure valid and reliable measures.

## **5. Research Methodology:**

### **Study design**

This methodological, descriptive study will be conducted in Shenzhen, Zhengzhou, Shanghai, mainland China, from November 2024 to April 2025. Pediatric oncology patients will be enrolled from inpatient ward in Shenzhen Children’s Hospital, Henan Cancer Hospital and Shanghai Children’s Medical Center.

This study will follow the Strengthening the Reporting of Observational Studies in Epidemiology (STROBE) reporting guideline.

### **Data collection**

Research team contacts with the dean of Nursing Department of each site. After approval, the name list of pediatric oncology patients receiving the neurotoxicity agents will be provided. Well-trained registered nurses will identify potentially eligible participants through checking the medical records and confirm the eligibility based on the inclusion and exclusion criteria. In addition, the registered nurse will approach these potential participants and ask all children and their parents who accompanied children for hospitalization in inpatient clinic or medical consultation in the outpatient clinic, and introduce the study. The information sheet including research purpose, procedures, confidentiality measures, and their rights as participants will be provided. All pediatric patients agree to participate the study will invite to sign an informed consent form with their legal guardian in accordance with the Declaration of Helsinki. We assure participants’ responses would remain confidential. After obtaining written consent, each child will be asked to complete the questionnaire independently. For those children who are unable to self-report, parents will

be asked to assist them in completing the questionnaire. To assess test-retest reliability, a sample of 50 children will be randomly selected to respond by phone to the P-CIN 2 weeks later.

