## **Participants**

Eligible participants are children 6 to 18 years of age[6] who (1) diagnosed with cancer, (2) had received or were currently receiving neurotoxic chemotherapy drugs (e.g., Vincristine, Cisplatin, Carboplatin, Oxaliplatin, Paclitaxel, Docetaxel, Ixabepilone, Bortezomib, Thalidomide), (3) children's, and parents' willingness to participate in the study voluntarily, (4) able to communicate, read, and write in Chinese without significant hearing and vision problems to ensure they understand our interview. The exclusion criteria are children who (1) diagnosis of a tumour involving the central nervous system (CNS) cancer, (2) diagnosis of relapsed cancer or secondary cancer, (3) in the terminal period, (4) plan to receive multiple cancer treatment (e.g., radiotherapy, immunotherapy), (5) suffering from other neuromuscular diseases (e.g., traumatic brain injury and cerebral palsy), (6) have a developmental deficit (e.g., Down's syndrome, other chromosomal disorders), (7) suffering from psychiatric diseases or using antipsychotic drugs, (8) severe cardiovascular system diseases and severe liver and kidney function abnormalities, (9) peripheral neuropathy symptoms caused by diabetes, genetic diseases, spinal cord injury, or alcoholism, (10) have other neuromuscular disorders (e.g., traumatic brain injury, cerebral palsy).

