## **CIPN measurements**

### ***Pediatric chemotherapy-induced peripheral neuropathy (P-CIN)***

It was originally developed for children  $\geq$  6 years old who had received or were receiving neurotoxic chemotherapy and reported peripheral neuropathy to quantify numbness and tingling in the hands and feet and the functional deficits in the past two to three days[6]. The P-CIN comprises 13 items, with eight items to rate CIPN symptoms in the hands and feet and five items to rate the difficulty of performing functional tasks, e.g., standing on one leg and closing eyes for 15 seconds[6]. Each item is rated using a 6-point faces scale. The total score ranges from 0 to 65 with higher scores indicating more severe CIPN[6].

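### The test-retest sub-study describes nothing at retest that would separate true change from measurement error in the ICC; one added question and a few recorded facts would do so cheaply

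*Protocol*

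**What the plan says.** **The retest.** The protocol, Data collection, states that "a sample of 50 children will be randomly selected to respond by phone to the P-CIN 2 weeks later". Reliability assessment repeats the 50, accepts an interval of 10 to 14 days, acknowledges that the interval affects how the result is read, and names the ICC. Data analysis treats an ICC of 0.70 as the minimum satisfactory value.

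**The first test.** Data collection says that "each child will be asked to complete the questionnaire independently", with a parent helping children who cannot self-report. It does not say whether this is on paper, on a screen or by interview. The Feasibility section has an item on whether the child needed help; its only stated use is for feasibility.

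**The instrument.** It has "13 self-reported items using age-appropriate language and graphics", and "Each item is rated using a 6-point faces scale". Recall covers the past two to three days.

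**Who can be drawn.** Candidates are found because "the name list of pediatric oncology patients receiving the neurotoxicity agents will be provided". Eligible children "had received or were currently receiving neurotoxic chemotherapy drugs". Study design places enrolment on inpatient wards, while Data collection also mentions children attending for "medical consultation in the outpatient clinic". The retest draw is random and is not limited to children expected to be stable.

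**Expected course.** Scope and Background says that severity may fluctuate during treatment and tends to rise, and that neuropathy can persist for months to years after treatment ends.

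**The concern.** A test-retest ICC estimates reliability only if the quantity measured stays the same between the two tests. Here some of the 50 may be under neurotoxic treatment, and the protocol's own background gives a reason to expect change in such children. With a recall of two to three days, the two reporting windows do not overlap, so the retest answers describe a different period. Nothing described at retest would show which children changed.

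True change would then lower the ICC and be read as instability of the Chinese P-CIN. A reliable scale could fall below 0.70, or be graded lower than it deserves. An analysis plan cannot fully repair this. Treatment between the tests can be read from medical records as a proxy, but a child's own rating of change cannot be recovered if it was never asked.

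A second, smaller matter is the phrase by phone. The scale is visual. On a voice call the child may not have the faces in view, and a parent may relay the questions or answers. If a smartphone form is meant, the problem largely disappears provided the same form is used at both tests. The protocol does not say which is meant.

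**Working it through.** **The plan's own figure.** The 50 children are tied to alpha 0.05 and power 0.90, but no null or alternative ICC is given, so the number can be neither confirmed nor refuted. With the usual formula for two measurements per child, n = 1 + 4(z_alpha + z_beta)² / (ln C)², where C = [(1+r0)/(1−r0)] / [(1+r1)/(1−r1)], a one-sided test gives 49 for r0 = 0 against r1 = 0.40, and also 49 for 0.50 against 0.75. Against r0 = 0.70, 50 children need a true ICC of about 0.86. The point below does not depend on this.

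**Effect of true change.** From the protocol: n = 50, two tests, threshold 0.70. Assumed, because the document gives neither: the reliability R of the scale in unchanged children, and the true-score stability s (the correlation of true scores between the two tests).

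- Expected ICC: r = R × s.
- For a one-way ICC with two measurements, F = (1+ICC)/(1−ICC), on n−1 = 49 and n = 50 degrees of freedom.
- An observed ICC of 0.70 corresponds to F = 1.70/0.30 = 5.67.
- Chance of reaching it: P(F(49,50) ≥ 5.67 × (1−r)/(1+r)).
- Example: R = 0.85 and s = 0.80 give r = 0.68, so the cut is 5.67 × 0.32/1.68 = 1.08 and the chance is 0.394.

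Each cell shows the expected ICC, then the chance of an observed ICC of at least 0.70:

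| R | s = 1 | s = 0.95 | s = 0.90 | s = 0.80 |
|---|---|---|---|---|
| 0.80 | 0.80; 95% | 0.76; 82% | 0.72; 61% | 0.64; 22% |
| 0.85 | 0.85; >99% | 0.81; 96% | 0.77; 84% | 0.68; 39% |
| 0.90 | 0.90; >99% | 0.86; >99% | 0.81; 97% | 0.72; 61% |

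A simulation at R = 0.85 (20,000 runs) gave 0.996, 0.962, 0.837 and 0.399, in agreement. A different model, which adds a change variance c at the retest (first-test variance set to 1), gives ICC = R/(1 + c/2). With R = 0.80 and c = 0.2 or 0.4 this is 0.80/1.1 = 0.73 or 0.80/1.2 = 0.67.

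**Effect of a constant mode shift.** Assume R = 0.85, no true change, and a shift of d SD between the tests. The expected agreement ICC is 0.85/(1 + d²/2):

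- d = 0.2: 0.85/1.02 = 0.83; simulated chance of at least 0.70, 99%.
- d = 0.3: 0.85/1.045 = 0.81; 98%.
- d = 0.5: 0.85/1.125 = 0.76; 82%.

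A consistency ICC is not affected by a constant shift.

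**Precision in an unchanged subset.** At an observed ICC of 0.80, F = 1.80/0.20 = 9. Dividing and multiplying by the 97.5% F points and converting back gives a 95% CI of 0.67 to 0.88 with 50 children, and 0.64 to 0.89 with 35. The 35 is an assumption.

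**The case against.** **Change within two weeks is conjecture.** The protocol did consider the interval, and the background statement about rising severity concerns treatment courses, not 14 days. No proportion on treatment and no short-term rate of change is given, and children whose treatment is past also qualify. This stands: how many of the 50 will change is unknown. It is also the reason to ask, since without the question it stays unknown after the study.

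**The effect is often small.** This stands too. At reliability 0.85 the chance of reaching 0.70 is 84% or more down to stability 0.90. In addition, 0.70 is an interpretive label; no decision in the protocol hangs on it.

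**A reader might infer that the retest uses a different mode from the first test.** The document does not establish that. The mode of the first test is not stated, the eligibility criteria speak of an interview, and the Background calls the original P-CIN "the first electronic CIPN patient reported outcome measure (PROM" so that by phone may mean a smartphone form. The phrase needs defining; no mismatch is shown.

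**A reader might also infer that respondents may switch between tests.** The text is only silent on this. The assistance rule stands just before the retest sentence and can be read as carrying over. Saying so costs nothing, but the silence is not an error.

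**Restricting the phone to reminders would be a stronger remedy than the text supports.** It trades one problem for others: lost retests, and parental help at home that staff do not see.

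**Conclusion.** The point holds as a worthwhile, inexpensive improvement. The protocol fixes a retest at about two weeks in a random draw that includes children on neurotoxic treatment, and describes nothing at retest that would separate true change from measurement error in an ICC judged against 0.70.

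The likely direction is downward: a reliable scale may look less stable than it is. The size cannot be computed from the document. Under the assumed values shown, the effect ranges from negligible when children are nearly stable to a chance below one half of reaching 0.70 when stability is 0.80 and reliability is 0.85 or lower. The documents do not support calling the retest invalid, claiming a proven change of mode, or expecting a false claim of reliability.

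**What to change.** In Data collection and Reliability assessment:

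1. Add one retest question: are symptoms the same, better or worse than at the first test?
2. Note from the medical records any neurotoxic treatment given between the tests.
3. Repeat the Feasibility section's assistance item at retest, and keep the same respondent and level of help as at the first test.
4. State what by phone means. If it is a smartphone form, use that form at both tests. If it is a voice call, make sure the child has the printed or on-screen faces scale in view during the call, and report the mode difference as a limitation.
5. Report the ICC with its 95% CI both in all retested children and in those reporting no change.

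**Cost.** One added question and a short look at the records, with no extra enrolment or retests. The interval in the unchanged subset is somewhat wider, as shown in the calculation. The change rating is subjective and selecting on it can raise the ICC, which is why both ICCs should be reported.

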## **Participants**

Eligible participants are children 6 to 18 years of age[6] who (1) diagnosed with cancer, (2) had received or were currently receiving neurotoxic chemotherapy drugs (e.g., Vincristine, Cisplatin, Carboplatin, Oxaliplatin, Paclitaxel, Docetaxel, Ixabepilone, Bortezomib, Thalidomide), (3) children's, and parents' willingness to participate in the study voluntarily, (4) able to communicate, read, and write in Chinese without significant hearing and vision problems to ensure they understand our interview. The exclusion criteria are children who (1) diagnosis of a tumour involving the central nervous system (CNS) cancer, (2) diagnosis of relapsed cancer or secondary cancer, (3) in the terminal period, (4) plan to receive multiple cancer treatment (e.g., radiotherapy, immunotherapy), (5) suffering from other neuromuscular diseases (e.g., traumatic brain injury and cerebral palsy), (6) have a developmental deficit (e.g., Down's syndrome, other chromosomal disorders), (7) suffering from psychiatric diseases or using antipsychotic drugs, (8) severe cardiovascular system diseases and severe liver and kidney function abnormalities, (9) peripheral neuropathy symptoms caused by diabetes, genetic diseases, spinal cord injury, or alcoholism, (10) have other neuromuscular disorders (e.g., traumatic brain injury, cerebral palsy).

## **Sample size**

Although there is no golden standard for the sample size calculation for validation study in nursing research, the recommended sample size for factor analyses is between 150 to 180.[7] In addition, the Exploratory Factor Analysis (EFA) and Confirmatory Factor Analysis (CFA) must be conducted on different datasets.[8] We therefore determined to recruit 300 pediatric oncology patients in our validation study.

## **CIPN measurements**

### ***Pediatric chemotherapy-induced peripheral neuropathy (P-CIN)***

It was originally developed for children  $\geq$  6 years old who had received or were receiving neurotoxic chemotherapy and reported peripheral neuropathy to quantify numbness and tingling in the hands and feet and the functional deficits in the past two to three days[6]. The P-CIN comprises 13 items, with eight items to rate CIPN symptoms in the hands and feet and five items to rate the difficulty of performing functional tasks, e.g., standing on one leg and closing eyes for 15 seconds[6]. Each item is rated using a 6-point faces scale. The total score ranges from 0 to 65 with higher scores indicating more severe CIPN[6].

### ***Clinician diagnosis of pediatric CIPN***

In our previous systematic review of assessment measures for CIPN among pediatric oncology patients(reference), it was concluded that the method of choice for assessing pediatric CIPN was combination of subjective and objective assessment measures. The diagnosis of pediatric CIPN in our study was established solely if the abnormal Nerve Conduction Studies (NCS) criteria, NCI-CTCAE score  $\geq 2$ , and clinical consultation (including the chemotherapeutic drugs used, cumulative doses, and clinical characteristics and time course of neuropathy symptoms) of CIPN symptoms were simultaneously observed based on the consensus of pediatric neurologists in the three hospitals.

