**(1) NCS criteria:**

For the NCS, the motor responses of median and ulnar nerves in the bilateral upper limb and the fibular and tibial nerves in the bilateral lower limb and the sensory responses of median and ulnar nerves in the bilateral upper limb and sural and medial plantar nerves in the bilateral lower limb were recorded. Nerve conduction parameters recorded included distal motor latency (DML), peak to peak sensory nerve action potential amplitude, motor nerve conduction velocity (MNCV), and sensory nerve conduction velocity (SNCV). Pediatric individuals who are at least 4 years old are deemed to have achieved the NCS reference ranges typically seen in adults.[14] The reference values for each nerve were according to reference limits of NCS parameters for Chinese subjects from Fong et al. as follows:

Table 1 Reference lists of NCS parameters for Chinese subjects and range in all subjects

Parameters	Reference limits	Range all subjects	
	Chinese		
Motor			
Median			
DML (ms)	4.1	2.5-4.3	
Amplitude (mV)	7.3	7.0-17.9	
MNCV (m/s)	52	50-65	
Ulnar			
DML (ms)	3.0	2.0-3.1	
Amplitude (mV)	6.4	6.3-15.6	
MNCV (m/s)	53	52-68	
Fibular			
DML (ms)	4.2	2.6-4.4	
Amplitude (mV)	3.3	2.4-10.9	
MNCV (m/s)	43	42-58	
Tibial			
DML (ms)	3.9	2.4-4.3	

Amplitude (mV)	7.5	5.1-26.7
MNCV (m/s)	41	38-57
Sensory		
Median		
Amplitude (mV)	7	5-34
SNCV (m/s)	48	45-67
Ulnar		
Amplitude (mV)	6	2-22
SNCV (m/s)	48	46-66
Sural		
Amplitude (mV)	6	2-34
SNCV (m/s)	42	38-61
Medial plantar		
Amplitude (mV)	3	2-37
SNCV (m/s)	40	26-36

NCS parameters including distal latencies, amplitudes, and velocities were considered abnormal, if values were more than 2.0 standard deviation of the normal reference values. In our study, the pediatric neurologist considered CIPN as the presence of abnormal NCS parameters in two or more nerves.

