## **(2) National Cancer Institute Common Terminology Criteria for Adverse Events (NCI-CTCAE) Version 5.0**

The CTCAE (version 5.0) consists of over 330 items scoring adverse events (AE) due to cancer treatment divided into 26 different categories. Grade refers to the severity of the adverse events. Possible grades range from grade 1 (Mild, asymptomatic or mild symptoms, clinical or diagnostic observations only), grade 2 (Moderate; minimal, local or noninvasive intervention indicated; limiting age-appropriate instrumental Activities of Daily Living (ADL)), grade 3 (Severe or medically significant but not immediately life-threatening; hospitalization or prolongation of hospitalization indicated; disabling; limiting self-care ADL), grade 4 (Life-threatening consequences; urgent intervention indicated) to grade 5 (Death related to AE). The NCI-CTCAE items used for the assessment of CIPN are peripheral sensory neuropathy, peripheral motor neuropathy, constipation, diarrhea, and neuralgia due to the sensory, motor and autonomic symptoms of pediatric CIPN[15]. The maximum CTCAE sum score of these 5 items is 22. Participants with a total score of 2 or higher are considered to have CIPN[16, 17].

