### ***Validity assessment***

Validity refers to an instrument measures exactly what it proposes to measure. Validity can be assessed in different forms such as content validity, convergent validity, criterion validity, and construct validity. **Content validity** can be defined as the extent to which an assessment tool accurately and fully reflects the concept being measured. The Delphi technique will be used to establish the content validity of the P-CIN. We will obtain the opinions of 10 experts through a structured questionnaires delivered two iterations until consensus will be reached. **Convergent validity** is the degree to which scores on a measure associate with scores on other measures that are intended assess similar constructs. Pain level, self-reported quality of life are CIPN-related concepts that have been identify pediatric oncology patients with CIPN risk[15]. Therefore, convergent validity will be explored using well-established CIPN-related measurements, namely, (1) the Wong-baker FACES pain rating scale to assess levels of pain; and (2) the Pediatric Quality of Life Inventory (PedsQL) Cancer Module to determine level of quality of life with the help of the Spearman's correlation coefficient (r). **Criterion validity** is the relation between the score of a certain instrument and some external criterion. This criterion has to be a widely accepted measure, with the same characteristics of the assessment tool. Criterion validity will be evaluated using the pediatric neurologists' CIPN diagnosis as a reference criterion. Spearman's correlation coefficient (r) will be calculated to evaluate the correlations between the P-CIN and the CIPN diagnosis. Using diagnostic testing to determine the presence or absence of the CIPN is essential. The ROC curve aims to find an optimal cut-off value with the best CIPN diagnostic performance. Additionally, the ROC curve is utilized to evaluate the overall diagnostic performance of a test and to compare multiple diagnostic tests.[23] The area under the curve (AUC) will be used to measure the accuracy of diagnostic test. Generally, an  $AUC \geq 0.8$  is considered acceptable. Youden statistic (calculated as sensitivity + specificity - 1) was used to determine the optimal cut-off value.[24] The point at which this value is maximized is determined as the optimal cut-off value.[24]

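### Two of the three legs of the reference diagnosis overlap in content with P-CIN, and the protocol sets neither masking nor timing between them, so the AUC and cut-off cannot be clearly interpreted.

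*Protocol*

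**What the plan says.** **Reference standard.** Under Clinician diagnosis of pediatric CIPN, a child has CIPN only if three things hold together: abnormal NCS, a CTCAE score of at least 2, and a clinical consultation. They must be such that they "were simultaneously observed based on the consensus of pediatric neurologists in the three hospitals". The consultation covers the drugs used, cumulative doses, and "clinical characteristics and time course of neuropathy symptoms". The NCS leg is the "presence of abnormal NCS parameters in two or more nerves". The CTCAE leg sums five items, "peripheral sensory neuropathy, peripheral motor neuropathy, constipation, diarrhea, and neuralgia", and the rule is: "Participants with a total score of 2 or higher are considered to have CIPN". The grade definitions in that section describe grades 2 and 3 by limits on daily activities.

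**Index test.** The P-CIN section says the instrument quantifies "numbness and tingling in the hands and feet and the functional deficits in the past two to three days". Eight of its 13 items rate symptoms and five rate difficulty with functional tasks.

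**Use.** The Validity assessment section takes the neurologists' "CIPN diagnosis as a reference criterion" for the Spearman correlation, and the ROC curve and Youden cut-off concern the same presence or absence of CIPN. It calls an AUC of 0.8 or more generally acceptable; Data analysis grades the AUC in bands.

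**Conduct.** Data collection says the child completes the questionnaire after consent. No section gives the order or interval relative to NCS, CTCAE or consultation, or says who may see the answers. Section 4 says: "The severity of CIPN may fluctuate during treatment courses".

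**The concern.** An AUC measures the accuracy of a questionnaire only if the reference is reached independently of it and describes the same state. Two features of the plan leave this open.

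1. **Shared content without masking.** The consultation and part of the CTCAE leg rest on symptoms and limits reported by the same child or parent who answers P-CIN. A child who over- or under-reports does so in both places. If raters can also see the P-CIN form, its answers can influence the diagnosis. Both effects raise the AUC and can move the cut-off.
2. **No interval.** P-CIN looks back two to three days, severity is said to fluctuate, and children with past or current exposure are eligible. If the diagnosis is made at another time, the two measures describe different states, which pulls the AUC down.

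The AUC and cut-off are what a clinic would use to adopt P-CIN. With two uncontrolled influences acting in opposite directions, a reader could not tell what the reported values mean. Masking and timing belong to study conduct: an analysis plan cannot restore them after data collection.

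**Working it through.** **No planned figure to reproduce.** The protocol gives no expected AUC. Its sample size of 300 is 2 × 150, one set for each factor analysis, and was not derived from the AUC.

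**Step 1: overlap by leg.**

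| Leg | Content | Overlap with P-CIN |
|---|---|---|
| NCS | latencies, amplitudes, velocities | none; no self-report |
| CTCAE sum | sensory and motor neuropathy, neuralgia, constipation, diarrhoea | partial |
| Consultation | drugs, doses, symptom characteristics and course | partial |

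**Step 2: does any text tie P-CIN to the diagnosis?** The word for simultaneity in the diagnosis section links the three legs to one another, not to P-CIN. No other section supplies a link.

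**Step 3: direction and size.** The protocol gives no inputs for this, so every parameter is an assumption. Let T be true neuropathy, and let all T and error terms be standard normal.

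- P-CIN = √0.5·T + √0.5·e
- Each symptom leg = √0.5·T + √0.5·(ρ·e + √(1−ρ²)·own error)
- NCS = √0.5·T + √0.5·independent error
- CIPN = all three legs above their cuts

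Here ρ is the correlation between the reporting error in P-CIN and that in each symptom leg. Simulated AUC of P-CIN against the composite:

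| Share positive on each leg | ρ = 0 | ρ = 0.25 | ρ = 0.5 | Rise |
|---|---|---|---|---|
| NCS 20%, symptom legs 70% (NCS dominates) | 0.77 | 0.79 | 0.80 | 0.02 to 0.03 |
| All legs 50% | 0.78 | 0.83 | 0.87 | 0.05 to 0.09 |
| NCS 70%, symptom legs 30% (symptom legs dominate) | 0.79 | 0.85 | 0.91 | 0.06 to 0.12 |

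In the last row the Youden point also moved, from about 0.3 to 0.5 standard deviations of the P-CIN score. In the first two rows it hardly moved.

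**Step 4: sight of P-CIN.** With all legs at 50% and ρ = 0, letting raters give the P-CIN score a weight of 25% or 50% in the two symptom legs raised the AUC from 0.78 to 0.84 or 0.89.

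**Step 5: time gap.** Let the true state at P-CIN correlate 0.9, 0.7 or 0.5 with that at diagnosis, all legs at 50%.

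- ρ = 0: the AUC falls from 0.78 to 0.75, 0.69 or 0.64.
- ρ = 0.5: it falls from 0.87 to 0.84, 0.78 or 0.72.

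With ρ = 0.5 and a lag correlation of 0.7 the AUC is 0.78, the same as with neither problem. The two biases can cancel, and the data would not show it.

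**Step 6: NCS alone as reference.** With all legs at 50% and no gap the AUC is 0.73 at every ρ, because NCS shares no reporting error. With no shared error the composite gives 0.78, so 0.78 − 0.73 = 0.05 of the difference arises only because one leg is a noisier reference than three.

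**The case against.** **P-CIN is not part of the reference.** A reader might infer that the diagnosis contains the same symptom report that P-CIN collects, which would be incorporation bias. The documents do not support that. The child answers P-CIN, neurologists reach the diagnosis by consensus, and nothing says one feeds the other. The overlap is also partial: the consultation covers drugs and doses, and two CTCAE items are bowel symptoms, which the described P-CIN content does not include. This stands. What remains is shared reporting error and possible sight of the answers.

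**NCS limits the inflation.** No child counts as a case without abnormal conduction in at least two nerves. This stands in part. A CTCAE sum of 2 out of a stated maximum of 22 can be reached by two grade 1 items, so lenient symptom legs are plausible. With NCS at 20% and symptom legs at 85% positive, the AUC goes only from 0.76 to 0.77 at ρ = 0.5. With NCS at 50% and symptom legs at 80% it goes from 0.755 to 0.797. Neither crosses 0.8. The relative strictness of the legs is unknown, so neither a negligible nor a large inflation can be ruled out.

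**The missing interval does not inflate the AUC.** A reader might also infer that it does. By itself a gap mainly lowers it; it could add to inflation only if an open order lets raters see P-CIN first.

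**0.8 is no gate.** The protocol calls it generally acceptable and labels 0.7 to 0.8 fair. No decision depends on it. This stands.

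**The composite is deliberate.** The protocol prefers combined subjective and objective assessment, and an NCS-only AUC answers a narrower question. This stands, so NCS alone should be a sensitivity analysis. Its absence from the protocol is not in itself a fault.

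**Conclusion.** The point holds as a weakness of design that should be corrected. The content overlap, the missing masking and the missing order and interval follow from the text and need no assumption. The direction of each effect is clear: shared error or sight of P-CIN raises the AUC, and a gap mainly lowers it.

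The size is not known. With half of each measure taken as error and ρ between 0.25 and 0.5, inflation is about 0.02 to 0.03 when NCS dominates and about 0.05 to 0.12 when the symptom legs weigh as much or more. It drops to about 0.01 if the symptom legs are very lenient. These figures illustrate and do not predict. The claim that a test truly below 0.8 will pass through shared error goes too far: it happens under some of these assumptions and not others. The supported conclusion is that the AUC and cut-off, obtained as the protocol now stands, could not be clearly interpreted.

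**What to change.** 1. State that P-CIN answers are withheld from the neurologists and CTCAE raters until the diagnosis is recorded.
2. State the order of assessments, and that P-CIN and the CTCAE/consultation are completed within the same P-CIN recall window. Record the NCS date so that its distance from P-CIN can be reported.
3. Keep the composite diagnosis as the main criterion and add one secondary AUC against the NCS criterion alone. Say in advance that it is a sensitivity analysis and that a lower value is expected, partly because a single leg is a noisier reference.

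Cost: a few sentences of procedure, somewhat tighter scheduling at three sites, and one extra ROC curve on data already collected. The sample size does not change and no new test is needed. The likely downside is a less flattering second AUC that has to be explained.
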